1. Protocol Title

Tofacitinib Hypothesis-generating, Pilot Study for Corticosteroid-Dependent Sarcoidosis

2. Objectives

This study will enroll 5 subjects with corticosteroid dependent pulmonary sarcoidosis.

The purpose of this pilot study is to determine if further research is warranted to assess if tofacitinib is an effective steroid sparing treatment for pulmonary sarcoidosis. The primary end point for this study is a 50% or greater reduction in corticosteroid requirement. We hypothesize that 60% of the patients will have a 50% or greater reduction in their steroid requirement without a significant decrease in pulmonary function testing and with a similar quality of life. We further hypothesize that STAT-1 dependent gene expression studies will show a significant decrease after tofacitinib treatment.

Objective 1: Test the hypothesis that the addition of tofacitinib will allow patients with sarcoidosis to have 50% or greater reduction in their corticosteroid requirement without a significant decrease in pulmonary function testing, and with a similar quality of life as measured by a validated questionnaire (1).

Objective 2: Test the hypothesis that the addition of tofacitinib will result in significantly decreased expression of STAT-1 dependent gene expression.

3. Background

Sarcoidosis is an inflammatory disorder of unclear etiology with a prevalence that has been estimated to be as high as 300/100,000. (2) The mainstay of treatment is oral corticosteroids. However, this therapy has numerous side effects and has been linked to increased relapses and poor quality of life, particularly at high doses. (3, 4) Furthermore, there is a subset of patients with persistent disease despite corticosteroid treatment. This has led to multiple trials evaluating various immunomodulatory agents for steroid sparing treatment in sarcoidosis. Our group and others have previously shown upregulation of the STAT1 pathway including the downstream cytokines in tissue, whole blood and lymph nodes of patients with sarcoidosis. (5-7)

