Tofacitinib is a janus kinase (JAK) inhibitor with a predominant effect on JAK1 and JAK3 which in turn decreases STAT1 activation. (8) Tofacitinib is currently FDA approved for treatment of psoriatic arthritis and rheumatoid arthritis and has recently shown superiority when compared to methotrexate as front-line therapy. It is similar to TNF-alpha inhibition when added as an adjunctive therapy. (9, 10) Other trials have shown efficacy in a number of other inflammatory disorders including ulcerative colitis. (11, 12)

Given the need for improved therapeutics, and the role of STAT1 in the pathogenesis of sarcoidosis, we propose a study examining the reduction in steroid use in patients who are dependent on a stable dose (defined as same dose for 4 weeks) of 15 mg/day to 30 mg/day of prednisone or its equivalent to control their disease. A recent query of OHSU's electronic medical record identified over 800 adult patients with sarcoidosis, generally 10-30% of patients with sarcoid require chronic treatment for an expected population of 80-240 eligible patients in our system. (13) We intend to enroll 5 patients with pulmonary sarcoidosis, age 18 or older of either gender in an open label proof-of-concept study design and treat with 5 mg of Tofacitinib BID for 16 weeks as a steroid sparing agent. We hypothesize that 60% of patients will have a 50% or greater reduction in their steroid requirements without a significant decrease (defined as less than 15% reduction in forced expiratory volume in 1 second (FEV1), forced vital capacity (FVC) or diffusing capacity for carbon monoxide (DLCO)) in pulmonary function testing and a similar quality of life as measured by the St. George's Respiratory Questionnaire (SGRQ).(1) A clinically significant change is defined as >4 units in the SGRQ. (14) Patients who respond by these criteria will be allowed to continue on the study drug for additional time up to 52 weeks. This small study will serve as a pilot and safety study; larger trials will ultimately be necessary to validate these results.

Page 1 of 13 Revised: 7/15/2019

4. Study Design

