This is a 16-week open-label, interventional, proof of concept, hypothesis-generating study. This study will enroll five subjects over the course of two years. Patients recruited for this study must have histologically proven sarcoidosis, evidence of pulmonary disease on chest imaging, and an FVC >50%. They must require a stable dose (defined by 4 weeks or more) of prednisone at least 15 mg/day or equivalent corticosteroid prior to enrollment in the study. The prednisone dose cannot exceed 30 mg/day. The above criteria should insure that this is a relatively uniform group of subjects. All subjects will receive Tofacitinib 5mg twice daily for 16 weeks. After four weeks on Tofacitinib, the corticosteroid will be tapered per a pre-defined protocol (attached); once a reduction of 50% has been achieved, any further taper will be per physician discretion. The schedule for corticosteroid taper is based on 30 plus years of experience and customary practice at the Oregon Health & Science University. The experience of the investigators has consistently demonstrated an inability to taper corticosteroid dosage in many patients with sarcoidosis unless an effective, alternative immunosuppressive has been added to the patient's regimen. Furthermore, higher doses of corticosteroids have consistently been correlated with the risk of infection. (15) Throughout the trial we will be monitoring blood counts, liver function tests, lipids, renal function, and pulmonary function testing. We will also evaluate STAT-1 activity through measurement of CXCL10 levels and RNA-Seq measurement of selected transcripts (see below) before and after Tofacitinib therapy. The primary endpoint is a 50% or greater reduction in steroids with no significant decrease in pulmonary function or quality of life. After 16 weeks, subjects who meet the primary end-point will be permitted an optional one year open-label extension.

5. Study Population

a. Number of Subjects

Five subjects with histologically proven sarcoidosis with pulmonary involvement and corticosteroid dependence will be enrolled in this trial.

b. Inclusion and Exclusion Criteria

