Inclusion Criteria: Subjects age 18 and older of either sex will be included. Subjects must meet the WASOG definition of pulmonary sarcoidosis. (16) They must have histologically proven sarcoidosis, evidence of Pulmonary sarcoidosis on chest radiograph (Stage I, II, III or IV) (17), an FVC >50%, and can have concomitant extrapulmonary disease. Subjects must require 15 mg to 30 mg/day prednisone or equivalent corticosteroid to control their sarcoidosis. Dose of prednisone must be stable for 4 weeks prior to enrollment in the study. Subjects may be taking methotrexate, but may not be taking other immunosuppressive or immunomodulatory treatments (see below).

Exclusion Criteria:

- Patients taking immunomodulatory medications other than methotrexate in the two months prior to the study period will not be included. This includes but is not limited to azathioprine, cyclophosphamide, leflunomide, mycophenolate mofetil, cyclosporine, tacrolimus, and biologic medications.
- Patients requiring >30 mg/day prednisone or its equivalent.
- Pregnant or lactating women will not be included.
- Subjects with the following blood dyscrasias will not be included:
 - Hemoglobin <9g/dL or Hematocrit <30%
 - White blood cell count <3.0 K/cu mm
 - o Absolute neutrophil count <1.2 K/cu mm
 - o Platelet count <100 K/cu mm
- Subjects with an estimated GFR ≤40 ml/min
- Subjects with a total bilirubin, AST, or ALT more than 1.5 times the upper limit of normal at screening.

- Severe, progressive, or uncontrolled chronic liver disease including fibrosis, cirrhosis, or recent or active hepatitis.
- History of any lymphoproliferative disorder such as Epstein Barr virus (EBV) related lymphoproliferative disorder, history of lymphoma, leukemia, or signs and symptoms suggest of current lymphatic disease.
- Current malignancy or history of malignancy, with the exception of adequately treated or excised non-metastatic basal cell or squamous cell cancer of the skin, or cervical carcinoma in situ.
- Have or have had an opportunistic infection (e.g., herpes zoster [shingles], cytomegalovirus, Pneumocystis carinii, aspergillosis and aspergilloma, histoplasmosis, or mycobacteria other than TB) within 6 months prior to screening.
- Have a known infection with human immunodeficiency virus (HIV)

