- Have current signs and symptoms of systemic lupus erythematosus, or severe, progressive, or uncontrolled renal, hepatic, hematologic, endocrine, pulmonary, cardiac (New York Heart Association class III or IV), neurologic, or cerebral diseases (with the exception of sarcoidosis).

Screening: Subjects will be recruited through the Oregon Health and Science University (OHSU) pulmonary, ophthalmology, rheumatology, and internal medicine clinics in addition to local community pulmonology clinics by referral. Review of OHSU medical records and Epic query will also be used to identify potential subjects. Pre-screening will take place first through chart review and then telephone interview. Subjects who are eligible for the trial after pre-screening will then be screened in person. At the screening visit subjects will receive informed consent as below. Health history and medications will be reviewed. Blood and/or urine samples will be collected, and pulmonary function testing will be done as per the baseline visit plan detailed below. Data from subjects who fail screening will be destroyed at the end of the study.

c. Vulnerable Populations

This study will not include children, pregnant women, neonates, prisoners, or decisionally impaired adults.

d. Setting

Subjects will be consented and samples will be drawn at the OHSU specialty clinics on the 3rd and 4th floors of the Physician's Pavilion. Spirometry will be performed in the pulmonary function lab in Multnomah Pavilion or Physician's Pavilion. Samples will be stored in a central repository as part of [name] laboratory.

RNA extraction and gene expression analyses will be performed by the OHSU Gene Profiling Shared Resource and the Massively Parallel Sequencing Shared Resource under the guidance of [name].

e. Recruitment Methods

Subjects will be recruited through the OHSU rheumatology, pulmonary, ophthalmology, and internal medicine clinics. Subjects referred from outside clinicians/scientists or self-referral will be allowed, but is expected to account for a minority of subjects. Postings on internet support groups for people living with sarcoidosis will also be used for recruitment. An Epic and medical record query will be used to identify potential subjects. Subjects will be contacted by phone. A copy of the phone script is attached.

f. Consent Process

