The consent process will take place in the OHSU pulmonary clinic or other appropriate OHSU clinic prior to any study procedures. [name], [name], or a member of their research team will be responsible for discussing the study and consent documents with study participants. Ample time will be provided to ask and answer questions. It will be emphasized that participation is entirely voluntary and that this will not affect ongoing clinical care. If needed, an interpreter will be provided for the consent process and subsequent study visits. There are no current plans to provide a translated consent. Written consent will be verified by study staff prior to any research procedures. The signed form will be kept in study binders.

Page 3 of 13 Revised: 7/15/2019

6. Procedures Involved

- Blood draw: A blood draw will be done at baseline and at weeks 2, 4, 8, 12, 16 (end of treatment). We estimate that the blood draw at baseline and week 16 will be approximately 15ml. We estimate that the blood draw at weeks 2, 4, 8, and 12 will be approximately 7.5ml.
- Urinalysis: Women will have a baseline urine pregnancy test.
- RNA Seq: at baseline and week 16 blood will be drawn for blood levels of CXCL10 and RNA-Seq to assess change in STAT1-dependent gene expression using a known STAT1 pathway analysis. This is genetic testing. Consent will be obtained using the attached consent from. We have chosen RNA-Seq because this is a discovery protocol and because we have expertise in the implementation of this technology with two funded, NIH RO1 proposals dependent on it. However, because this study is based on just 5 paired samples and we wish to minimize multiple statistical comparisons, we will perform a paired T test on 14 transcripts which we have previously shown to be up regulated in the blood of patients with sarcoidosis and which are downstream of STAT-1 (including STAT-1 itself).⁷ These transcripts are A2M, WARS, CCND1, STAT-1, MT-1, TRH, CD64, IRF1, PSMB9, MHC2TA, OPRM1, Pim-1, CXCL9, and CDKN1A. The thousands of additional transcripts detected by RNA Seq will be analyzed, but in all cases, changes in expression will be considered as a preliminary observation which requires validation.
- Pulmonary function testing: At baseline and at the end of treatment (week 16), we will measure spirometry with DLCO. At weeks 4, 8, and 12 we will measure spirometry only.

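### Objective 2 credits tofacitinib with a baseline-to-week-16 biomarker change that also contains the steroid taper, and no on-drug biomarker sample precedes the taper

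*Combined protocol and SAP*

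**What the plan says.** Section 2 states Objective 2 as a test that "the addition of tofacitinib will result in significantly decreased expression of STAT-1 dependent gene expression". Section 8 adds CXCL10 under the same objective and specifies paired t tests of baseline against week 16, with p<0.05 as the criterion.

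On sampling, Section 6 says that "at baseline and week 16 blood will be drawn for blood levels of CXCL10 and RNA-Seq to assess change in STAT1-dependent gene expression". The CXCL10 and RNA Seq rows of the schedule table carry marks at those two visits only. Blood is taken more often than that: "A blood draw will be done at baseline and at weeks 2, 4, 8, 12, 16 (end of treatment"). At weeks 2, 4, 8 and 12 the table assigns only safety chemistry, lipids and blood counts.

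On steroids, Section 5b requires dependence at entry: "Subjects must require 15 mg to 30 mg/day prednisone or equivalent corticosteroid to control their sarcoidosis". Section 4 says: "After four weeks on Tofacitinib, the corticosteroid will be tapered per a pre-defined protocol (attached"). The schedule table also places the start of the taper at week 4. Once the dose has been halved, "any further taper will be per physician discretion".

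On interpretation, Section 3 says that "larger trials will ultimately be necessary to validate these results", and Section 6 treats expression changes as preliminary and in need of validation. Neither caveat mentions the taper.

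**The concern.** Two things change between the samples: tofacitinib is started and prednisone is reduced. Objective 2 names only the first. Subjects who succeed on the primary endpoint are those with the largest steroid change, so success on Objective 1 enlarges the second component of the Objective 2 contrast. That component can also vary between subjects, because taper past the halfway mark is discretionary.

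At stake is what the mechanistic result can say when the sponsor decides whether further research is warranted. If stepping down prednisone lets disease activity rise, a real drug effect on CXCL10 could be cancelled by week 16, and the study would report no pathway suppression. This is bias, not imprecision: a larger study with the same two samples would reproduce it.

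**Working it through.** The plan gives no effect size, SD or power for Objective 2, so there is no figure to reproduce. The check is mainly one of timing.

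**Timeline (Sections 4 and 6)**

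| Time | Tofacitinib | Prednisone | CXCL10 and RNA |
|---|---|---|---|
| Baseline (0-4 weeks before week 0) | none | 15-30 mg/day, stable | sampled |
| Weeks 0-4 | on | taper not yet started | not sampled, though blood is drawn at weeks 2 and 4 |
| Weeks 4-16 | on | tapering | not sampled until week 16 |
| Week 16 | end of treatment | reduced | sampled |

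- The taper can occupy 16 - 4 = 12 of the 16 on-drug weeks, or 12/16 = 75%.
- At the 50% target, 15 x 0.5 = 7.5 and 30 x 0.5 = 15, so a responder is at 7.5-15 mg/day or less at the second sample.
- On-drug biomarker samples before the taper: none.

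**What the test estimates.** Write each subject's week-16 change as drug effect + taper effect + time trend and noise. The paired t test averages the whole sum. Section 8 contains nothing that separates the first two terms.

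**Direction.** Section 5b says subjects need prednisone to control their disease, and Section 8 says CXCL10 is associated with severity. Together these suggest that less steroid could mean more disease activity and higher CXCL10, which opposes the hypothesised decrease. This is an inference. It covers CXCL10 and not the transcripts, and no passage gives a size. No passage points the other way, but none rules it out.

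**Illustration, all effects assumed.** With n = 5, df = 4, two-sided 0.05 (the plan does not state sidedness) and critical t = 2.776, P(significant decrease) is the noncentral t probability below -2.776 with noncentrality (net change in SD of the paired difference) x √5. If the drug lowers the marker by 1.0 SD, this is 40% with no taper effect and 14% if the taper raises the marker by 0.5 SD.

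**Precision of an early contrast.** The 95% CI half-width for a mean paired change is 2.776/√5 = 1.24 SD.

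**Intervals.** Baseline may precede week 0 by up to 4 weeks. Baseline to week 16 therefore spans 16-20 weeks, baseline to week 4 spans 4-8 weeks, and baseline to week 2 spans 2-6 weeks.

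**The case against.** The taper is not hidden. This is a steroid-sparing study, the taper is what the primary endpoint measures, and Section 4 says many patients cannot taper unless an effective alternative is added. One can fairly read the addition of tofacitinib as shorthand for that whole strategy, in which case week 16 measures what was intended. The study also calls itself hypothesis-generating and carries the caveats noted above. This much stands: it makes the point one of labelling and keeps it small. But Objective 2 is worded as a test of the drug, and no caveat names the taper.

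It is also true that n = 5 makes a null result weak anyway. In the illustration, 60% of trials miss a 1.0 SD drug effect with no taper effect at all. That stands too. The taper adds a separate problem that more subjects would not cure.

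A reader might infer that a week-16 decrease would be an artefact of the taper. The documents do not support that. The only direction they suggest works against a decrease, so in that direction a decrease would remain informative. A reader might also infer that an early sample would isolate the effect of tofacitinib. It would not: without a control arm, time trend and regression to the mean remain in any before-after contrast.

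Finally, the percentages rest on assumed effects and on a constant taper shift with fixed SD. They show a mechanism and are not evidence about this trial.

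**Conclusion.** The point holds as a mismatch between objective and contrast. The planned comparison estimates tofacitinib plus steroid reduction, while the plan labels it an effect of adding tofacitinib. That conclusion follows from the schedule alone and needs no assumed figure.

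The size and sign of the taper's contribution are not established. On the documents' own hints, which reach only CXCL10, the likelier harm is a masked drug effect and so a null result that cannot be interpreted. A decrease is not strictly specific to tofacitinib, but nothing in the documents suggests it would be spurious.

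Severity is minor to moderate: a secondary objective in a five-subject hypothesis-generating pilot, with a correction that is nearly free. The taper protocol is described as an attachment and was not in the text reviewed, so this rests on the week 4 start given in Section 4 and in the schedule table.

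**What to change.** 1. Reword Objective 2 in Section 2 and its analysis in Section 8 as the change under tofacitinib plus the protocol steroid taper. State that a null result does not exclude a drug effect and that a decrease is not specific to tofacitinib. Cost: text only.

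2. List each subject's prednisone dose beside each biomarker value. The information should already be in hand: at screening "Health history and medications will be reviewed", the schedule includes medication reconciliation, and the primary endpoint needs the doses. Cost: one listing.

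3. Add a CXCL10 assay to the scheduled week 4 draw, taken before the first reduced steroid dose, or to the week 2 draw. Report individual values and the mean change with its 95% CI, as a contrast without the taper and with no added hypothesis test. Cost: five assays, a consent line and a small extra blood volume. Planned blood is 2 x 15 + 4 x 7.5 = 60 ml per subject. The larger draws exceed the smaller by 15 - 7.5 = 7.5 ml, so allowing that much for the extra tubes gives at most about 67.5 ml. No extra visit is needed.

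State the limits of item 3:

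- The transcripts stay confounded unless an RNA tube is also drawn, and the documents give no sequencing cost.
- The early sample may precede the full drug effect.
- Unchanged prednisone from baseline to week 4 is implied by the schedule and not stated, so the dose listing should confirm it.
- Precision is poor at n = 5, and the sample does not replace a control.

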Long term follow-up: Patients who do not meet the primary end point will not be followed long term. Patients who meet the primary endpoint will be continued on study drug for up to one year. During that one year they will be followed with labs (CBC, BMP, liver function panel, lipid panel) every two months, and the above questionnaires and adverse event reporting by phone every three months. A clinic visit will be required every 6 months. Labs done during the one-year extension period will be billed to the patient's insurance; study drug will be covered by Pfizer.

Voluntary withdrawal from the study: Subjects may withdraw from the intervention (study drug Tofacitinib) at any time. For subjects who choose to withdraw from the intervention we will collect the following data two weeks after withdrawal from the intervention: CBC, lipid measurement, LFT, BMP, adverse event reporting.

Treatment with Tofacitanib to be discontinued and the patient withdrawn from this study for:

- Serious infections (those requiring parenteral antimicrobial therapy or hospitalization)
- A decline in glomerular filtration rate of 33% or greater
- An increase in liver function tests (LFTs) >2.5x the upper limit of normal
- Neutrophil counts <1000 neutrophils/mm3
- Platelet counts <100,000 platelets/mm3
- Any single hemoglobin value <8.0 g/dL or one that drops ≥2 gm/dL below baseline
- Other serious or severe AEs that the investigator believes are sufficient to discontinue the medication
- Extrapulmonary disease such as uveitis with substantial worsening despite tofacitinib therapy as determined by another health care provider

7. Data and Specimens

a. Handling of Data and Specimens

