The primary endpoint will be a 50% reduction in corticosteroid requirement in at least 60% subjects (or 3/5 of the subjects) by week 16, without significant decline in their pulmonary function—defined as a >15% decline in FVC, FEV1, or DLCO relative to the baseline value.

Objective 2:

The secondary endpoints include significant decreases in of peripheral markers of STAT pathway activity using RNA sequencing and CXCL10 levels, both measured before and after 16 weeks of tofacitinib treatment.

RNA sequencing will be done using before the study drug is started, and at week 16. We will evaluate STAT1-dependent gene expression as detected in our prior publication. (18) In our previous study, we found that of the 13/18 genes known to be downstream of STAT1 were upregulated in the peripheral blood of sarcoidosis patients (WARS, A2M, CCND1, CD64, MT-1, TRH, IRF-1, PSMB9, MHC2TA, OPRM1, Pim-1, CXCL9, and CDKN1A). We expect these 13 genes to be upregulated in the blood of pre-treatment subjects, and expect this expression level to significantly decrease in post-treatment subjects. An additional 8 genes in the JAK-STAT pathway were also found to be upregulated (IFNAR1, IFNAR2, IFNAR3, JAK1, JAK2, STAT1, STAT2, and STAT3). In a rheumatoid arthritis study of synovial biopsies before and after tofacitinib, STAT1 and STAT3 were found to be significantly decreased after tofacitinib treatment. (19) Interferon alpha receptors (IFNAR) are located upstream of the JAK-STAT pathway, and whether these expression profiles are expected to change is less clear. Expression of JAK 1, JAK2, STAT1, STAT2, and STAT3 are expected to significantly decrease with tofacitinib therapy. A paired T test will be used to compare expression levels at baseline and after 16 weeks of treatment, where a p<0.05 will be considered significant.

Finally, we will be measuring peripheral CXCL10 levels. STAT1 activation leads to CXCL10 transcription, making CXCL10 a valuable peripheral marker of JAK-STAT pathway suppression. (20) Serum levels of CXCL10 have been found to be elevated in the peripheral blood of patients with sarcoidosis, and were also be found to be associated with severity and chronicity of disease. (21) Peripheral expression of CXCL10 in the rheumatoid arthritis has been found to decrease after treatment with tofacitinib. (19) A pair T-test will be used to compare peripheral CXCL10 levels before and after 16 weeks of treatment, where a p<0.05 will be considered significant.

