- Adverse reactions occurring in controlled and open-label extension studies include:
 - o Blood and lymphatic system disorders: Anemia
 - Infections and infestations: Diverticulitis
 - Metabolism and nutrition disorders: Dehydration
 - Psychiatric disorders: Insomnia
 - Nervous system disorders: Paresthesia
 - o Respiratory, thoracic and mediastinal disorders: Dyspnea, cough, sinus congestion
 - Gastrointestinal disorders: Abdominal pain, dyspepsia, vomiting, gastritis, nausea
 - Hepatobiliary disorders: Hepatic steatosis
 - O Skin and subcutaneous tissue disorders: Rash, erythema, pruritus
 - Musculoskeletal, connective tissue and bone disorders: Musculoskeletal pain, arthralgia, tendonitis, joint swelling

- Neoplasms benign, malignant and unspecified (including cysts and polyps): Non-melanoma skin cancers
- o General disorders and administration site conditions: Pyrexia, fatigue, peripheral edema
- Pregnancy and Teratogenic effects: Pregnancy Category C. Pregnant and breastfeeding women will not be included in this trial.

b. Potential Benefits to Subjects

The purpose of this trial is to determine if Tofacitinib is an effective therapy in sarcoidosis. If this therapy is effective, subjects may see a symptomatic improvement and a reduction in corticosteroid requirement. Subjects who meet the primary endpoint will go on to a one-year extension where they will be given the study drug free of cost.

12. Resources Available

This study involves RNA extraction and RNA sequencing, which requires special resources through the Gene Profiling Shared Resource (GPSR). [name] is the director of the GPSR and will be assisting with this study.

13. Drugs or Devices

We will follow the applicable Research Pharmacy policies and procedures and provide Research Pharmacy with a pharmacy manual for the study.

References

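### Section 8 leaves quality of life out of a primary endpoint that the protocol defines in three different ways, so the analysis as written does not test Objective 1

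*Combined protocol and SAP*

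**What the plan says.** Three sentences say by name what the primary endpoint is, and no two agree.

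- **Section 2, Objectives:** the opening paragraph gives a steroid reduction of at least half and nothing else.
- **Section 4, Study Design:** "The primary endpoint is a 50% or greater reduction in steroids with no significant decrease in pulmonary function or quality of life".
- **Section 8, Data Analysis, Objective 1:** "a 50% reduction in corticosteroid requirement in at least 60% subjects (or 3/5 of the subjects) by week 16", without a significant lung-function decline, "defined as a >15% decline in FVC, FEV1, or DLCO relative to the baseline value".

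Objective 1 in Section 2 asks for the steroid reduction "without a significant decrease in pulmonary function testing, and with a similar quality of life as measured by a validated questionnaire". The 60% hypotheses in Sections 2 and 3 also carry a quality-of-life condition. Section 3 supplies its threshold: "A clinically significant change is defined as >4 units in the SGRQ".

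Section 8 does not take quality of life up elsewhere. Under Objective 2 it says: "The secondary endpoints include significant decreases in of peripheral markers of STAT pathway activity using RNA sequencing and CXCL10 levels". The SGRQ does not appear in Section 8.

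The endpoint also has a consequence for individual patients. Section 6, under long-term follow-up, says: "Patients who meet the primary endpoint will be continued on study drug for up to one year". Section 11b says: "Subjects who meet the primary endpoint will go on to a one-year extension". Neither passage defines the endpoint where it uses it.

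**The concern.** Section 8 is what an analyst will follow. Read literally, it counts as a success a patient who halves the steroid dose and keeps lung function but has a significant decrease in quality of life. Section 4 counts the same patient as a failure. Objective 1 asks whether steroids can be reduced without that cost, so a count that ignores quality of life answers a different question.

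Two things are at stake. The 3-of-5 count is the only stated success rule for Objective 1, and the study's declared purpose is to decide whether further research is warranted. In an open-label study of five patients, three competing definitions also leave room to settle on one after the outcomes are known.

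**Working it through.** **1. The plan's own figure.** 0.60 × 5 = 3, so 3/5 is 60% and Section 8's arithmetic is right. The next count down is 2/5 = 40%, which misses the threshold.

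**2. The definitions side by side.**

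| Source | Steroid reduction | Lung function | Quality of life | 60% or 3/5 |
|---|---|---|---|---|
| Section 2, named endpoint | yes | no | no | no |
| Section 4, named endpoint | yes | yes, limit not given | yes, no decrease | no |
| Section 8, named endpoint | yes | yes, >15% decline | no | yes |
| Section 2, Objective 1 | yes | yes, limit not given | yes, similar | no |
| Sections 2 and 3, hypotheses | yes | yes (Section 3 gives a 15% figure) | yes, similar | yes |

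Section 8 places its endpoint under Objective 1 but lacks one of that objective's three conditions. The secondary endpoints do not restore it.

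**3. What the omission can do to the result.** Two linking conditions are needed:

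- (a) The 3/5 threshold is applied to Section 4's patient-level definition. Section 4 does not state a threshold, but the Section 3 hypothesis joins 60%, lung function and SGRQ in one sentence.
- (b) The same >15% lung-function limit is used in both definitions.

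Let k be the number of patients who meet Section 8's conditions, and m the number of those k with a significant quality-of-life decrease.

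- Section 8 criterion met: k ≥ 3.
- Criterion with quality of life met: k − m ≥ 3.
- Verdict reversed: k ≥ 3 and m ≥ k − 2.

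| k | Smallest m that reverses | Count with quality of life |
|---|---|---|
| 3 | 1 | 3 − 1 = 2, or 2/5 = 40% |
| 4 | 2 | 4 − 2 = 2, or 2/5 = 40% |
| 5 | 3 | 5 − 3 = 2, or 2/5 = 40% |

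Under (a) and (b), an added condition can only remove responders, so any disagreement has Section 8 passing and the composite failing.

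**4. What is not defined.** The >4-unit SGRQ threshold has no direction. Section 4's wording suggests that only a worsening counts; *similar* in Sections 2 and 3 could mean any change. The documents do not say which score direction is worsening. The schedule has SGRQ at baseline and at weeks 2, 4, 8, 12 and 16, and none of the five later visits is named as the comparison.

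**5. What cannot be calculated.** A disagreement rate needs the share of Section 8 responders who lose quality of life, and the documents give none. They also give no null rate, alpha or power for the primary endpoint. The p<0.05 criterion belongs only to the paired t tests of gene expression and CXCL10.

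**The case against.** The strongest reply is that this is a five-patient, hypothesis-generating pilot with no formal test of the primary endpoint, and that the protocol itself says larger trials will be needed. SGRQ is collected throughout and a threshold exists, so both counts could be reported from the planned data. Nothing is lost and no test is biased. That is correct, and it limits the harm to an ambiguous success label and an ambiguous extension gate. It does not tell the analyst which count is primary.

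A second reply is that Section 8 is not clearly the odd one out. Two of the three sentences that name the endpoint omit quality of life, and Objective 1 is worded as a hypothesis. This stands as a reason to cite and reconcile all three. But Section 8 presents its endpoint as the analysis of Objective 1, and Objective 1 and both 60% hypotheses include quality of life, so the composite has the better support.

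A reader might infer that Section 4 itself fails a trial at 2/5. It does not, because it contains no 60% or 3/5 rule; that verdict needs linking condition (a).

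A reader might also infer that Section 8 is always the easier criterion. That holds only under condition (b). Section 4 leaves a significant lung-function decrease undefined, and the Section 3 parenthesis, read literally, equates it with a fall of under 15%, which conflicts with Section 8.

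**Conclusion.** The inconsistency is real and lies in current, complete text. The protocol gives three named primary endpoints, and the one in the analysis section omits a condition of the objective it is meant to test. With exactly three Section 8 responders, a single quality-of-life failure is enough to reverse the trial-level conclusion. This rests on the two linking conditions in the working and on no assumed rates. It is a possible outcome, not a predicted one.

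It would be tempting to size the problem by the chance of landing on exactly three responders, or by counting the combinations in which the definitions differ. Neither measures disagreement, because neither contains a quality-of-life failure rate. No claim about type I error or power follows either.

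**What to change.** Before outcomes are known, amend Section 8 to one patient-level responder definition that matches Objective 1 and Section 4:

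- a steroid reduction of at least 50%;
- no decline of more than 15% from baseline in FVC, FEV1 or DLCO;
- the quality-of-life condition, using Section 3's threshold of more than 4 SGRQ units.

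The sponsor must state whether only worsening counts or any change, which score direction is worsening, and which visit is compared with baseline. Apply the at-least-3-of-5 criterion to that definition, and report each component for each patient. Align the steroid-only sentence in Section 2 and the 15% parenthesis in Section 3 with it.

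The passages that tie the extension to the primary endpoint or to response criteria (Sections 3, 4, 6 and 11b) must be reconciled by the sponsor. This point does not say who should continue on study drug.

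The cost is protocol wording. SGRQ is already scheduled at baseline and five later visits, and spirometry with DLCO at baseline and week 16. The downside is a stricter criterion than Section 8's, so the result may look less favourable. A 3-of-5 rule will still turn on one patient; the change removes only the doubt over which patients count.
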